PI Principal Investigator
PRP Platelet rich plasma
RP Radical Prostatectomy

PSA Prostate-Specific Antigen

SAE Serious Adverse Event/Serious Adverse Experience

SHIM Sexual Health Inventory for Men SOP Standard Operating Procedure

Study Summary

Title	A Study Evaluating Intraoperative Application of Platelet-Rich Plasma to the Neurovascular Bundles During Nerve-Sparing Radical Prostatectomy: Initial Technical Description and Prospective Early Postoperative Outcomes Analysis					
Running Title	PRP Application During RP					
Protocol Number	16-001320					
Methodology	Open label					
Overall Study Duration	18 months					
Subject Participation Duration	18 months					
Single or Multi-Site	Single site					
Objectives	To evaluate the safety, tolerability, feasibility and efficacy of using platelet rich plasma to facilitate early nerve healing and decrease erectile dysfunction after nerve-sparing radical prostatectomy.					
Number of Subjects	20					
Diagnosis and Main Inclusion Criteria	Post-surgical erectile and urinary dysfunction. Main inclusion criteria are men, aged 50-60 years, with normal sexual function and regular sexual partner, undergoing RP for newly diagnosed prostatic adenocarcinoma.					
Study Product, Dose, Route, Regimen	Autologous Platelet-Rich Plasma The dose is approximately 1,000,000 platelets/mL and the product is applied topically to the neurovascular bundle once during radical prostatectomy					
Duration of Administration	One time drug administration with duration of drug application is approximately 4 hours.					
Reference therapy	None					
Statistical Methodology	The safety evaluation will focus on the number of adverse events including local reactions, expected serious adverse events and unexpected serious adverse events. All events will be collected, recorded and assessed for severity as a means to facilitate the reporting process. All patients will undergo an assessment of sexual and urinary function and oncologic outcomes at 3, 6, 9, 12 and 18 months after surgery. All patients will be evaluated for perioperative complications, length of stay, and need for blood transfusion.					

Version 4.0

1 Introduction

This document is a protocol for a human research study. This study will be carried out in accordance with the applicable United States government regulations and Mayo Clinic research policies and procedures. The described study will be conducted in compliance with the protocol and associated Federal regulations, and all applicable institutional research requirements.

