3.2 Primary Study Endpoints

Primary Objective:

To evaluate the safety and tolerability of using platelet rich plasma on the NVB after nervesparing radical prostatectomy.

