4.4 Early Withdrawal of Subjects

4.4.1 When and How to Withdraw Subjects

A subject may withdraw at any time prior to RP. There are no adverse safety considerations in the study for those deciding to withdraw from the study. Subjects may choose to discontinue study participation after RP surgery and will be counted as withdrawn

A subject consenting to the study will receive PRP at the time of RP unless the surgical team decides intra-operatively to withdraw a subject from the study in the following situations:

- Estimated blood loss greater than 750 mL
- Evidence of disease grossly and/or pathologically that the prostate cancer is locally advanced or metastatic

• Documentation of the reason for withdrawal will be retained in the study files.

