4.4.2 Data Collection and Follow-up for Withdrawn Subjects

As part of normal clinical care, subjects that have withdrawn from the study will still have routine postoperative monitoring after RP. Any collected study data from withdrawn subjects will not be included in the data analysis. Since all patients have their outcomes tracked after RP at Mayo Clinic, postoperative data would be available should this be needed as part of another study protocol.

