7.1 Sample Size Determination

For the proposed trial, a sample of 20 subjects is proposed. This sample will permit a statistical description of that is required for the primary and secondary objectives. Use of 20 subjects is in the range normally enrolled for trials of this nature.

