7.2 Statistical Methods

Descriptive Statistics

Univariate descriptive statistics and frequency distributions will be calculated, as appropriate for all variables. Baseline values for demographic, clinical, and outcome variables (primary and secondary) will be tabulated. Temporal trends in recovery of erectile function and urinary continence will be assessed. Normal sexual function will be defined as a Sexual Health Inventory for Men score of >19. Normal urinary continence will be defined as a response of "none" on question 5 of the Expanded Prostate Cancer Index Composite.

Handling of Missing Data

Subjects that miss follow-up appointments where data is gathered will be contacted to forward missing data records.

Multiplicity

Not applicable

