7.3 Subject Population(s) for Analysis

Data from all subjects consented for the study and completing postoperative visits will be evaluated.

² Vitals will be abstracted from the medical record for visit 3, post-operative day 2

³ Week 1 and week 12 visits may be done on-site or via telephone interview or email. Physical exam and vitals will be performed for these visits if participant is able to return to Mayo Clinic. Outside records for physical exam and vitals will be requested if visits are done remotely.

⁴ The 6, 9, 12 and 18 Month visits may be done remotely via telephone interview or email. Completed SHIM/EPIC Questionnaires may be returned to study site by mail, email or fax. PSA testing: A local clinic may be used for venipuncture, using mail in lab kit for sample return to Mayo Clinic. PSA testing window for week 12 and 6, 9, 12, 18 month visit is +/- 21d

8 Safety and Adverse Events

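### The primary safety summary is a count of adverse events; section 7 commits to neither the proportion of treated men affected nor an interval

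*Combined protocol and SAP*

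**What the plan says.** Section 3.2 gives the primary endpoint by repeating the objective: "To evaluate the safety and tolerability of using platelet rich plasma on the NVB after nervesparing radical prostatectomy". It names no measurable quantity.

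The one description of how safety will be summarised is in the Statistical Methodology row of the Study Summary: "The safety evaluation will focus on the number of adverse events including local reactions, expected serious adverse events and unexpected serious adverse events". The same row adds that perioperative complications, length of stay and need for transfusion will be evaluated in all patients.

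Section 7.2 is generic: "Univariate descriptive statistics and frequency distributions will be calculated, as appropriate for all variables". It mentions no interval and no confidence level. Section 7.1 says the sample allows the description that the primary objective requires, and supports this with: "Use of 20 subjects is in the range normally enrolled for trials of this nature".

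The denominator is set in several places:

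- Section 7.3: "Data from all subjects consented for the study and completing postoperative visits will be evaluated".
- Section 4.4.1: "Subjects may choose to discontinue study participation after RP surgery and will be counted as withdrawn".
- Section 4.4.2: "Any collected study data from withdrawn subjects will not be included in the data analysis".
- Section 4.4.3: men who withdraw are replaced until 20 have completed 18 months.

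Sections 3.1 and 8.6 plan to judge safety against registry men who had the same operation without PRP. They state no safety measure, margin or method.

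**The concern.** There are two separate problems.

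The first arises when events occur. A count does not say how many men were affected. Adverse events are collected for 18 months (section 8.1), so repeat events in one man are plausible. A comparison with registry men needs a proportion of men in each group, and the planned measure does not supply one.

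The second arises when a category is empty. A report of no local reactions or no unexpected serious events, without an interval, leaves the reader to judge what 20 men can rule out, and section 7.1 gives no help.

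A related question is which men are counted. Under 4.4.2, 4.4.3 and 7.3, a man who receives PRP, has an event and then withdraws is removed from the analysis and replaced. A per-man proportion built on those rules would describe men who stayed, not men who were treated.

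**Working it through.** **The plan's own figure.** The sample size is 20 (section 7.1). No event rate, precision, confidence level or power is given, so there is no calculation to reproduce.

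**Inputs.** N = 20, single arm (7.1, 3.1). Transfusion risk after RP of <1 to 5% (section 1.5). The 95% level is my assumption because the documents give none. Intervals are exact (Clopper-Pearson).

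**Zero affected men in 20.**

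- Two-sided 95% upper limit: 1 − 0.025^(1/20) = 0.168, or 16.8%.
- One-sided 95% upper limit: 1 − 0.05^(1/20) = 0.139, or 13.9%.
- Against the protocol's highest transfusion figure: 16.8 / 5 = 3.4, so the two-sided limit is more than three times that figure.

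**Chance that 20 men show no affected man**, (1 − p)^20:

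| True risk p | No affected man | At least one |
|---|---|---|
| 1% | 82% | 18% |
| 5% | 36% | 64% |
| 10% | 12% | 88% |
| 15% | 3.9% | 96% |

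**Same count, different risks.** Suppose five events are reported (illustrative):

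- All in one man: 1/20 = 5%, CI 0.1 to 24.9%.
- One in each of five men: 5/20 = 25%, CI 8.7 to 49.1%.

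The count is 5 in both cases, while the per-man risk differs fivefold.

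**Effect of the denominator.** Suppose 22 men receive PRP, two have an event and then withdraw, and the 20 completers have none (illustrative; the documents give no withdrawal rate):

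- Under 4.4.2, 4.4.3 and 7.3: 0/20, upper limit 16.8%.
- All treated men: 2/22 = 9.1%, CI 1.1 to 29.2%.

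**The case against.** The strongest reply is that the Study Summary line is synopsis wording and that a focus is not an exclusive choice. Section 7.2's frequency distributions for all variables would allow a table of men with an event. Section 8.3.1 records each event against an identified subject with severity, relatedness and expectedness, so per-man risks can be recovered. All of this stands: the plan is unspecific and does not rule out a per-man analysis. It does not commit to one either, and the one sentence specific to safety points to counts.

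Three stronger readings are tempting, and the documents do not support them.

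- A reader might infer that counting events instead of men makes a clean result look safer. It does not: with zero events, the event count and the number of affected men are both zero. In that case only the missing interval and the completer denominator matter.
- A reader might infer that the plan's safety results cannot be set against any benchmark. That is too broad. Transfusion and oncologic outcomes are assessed in all patients, and section 1.5 gives per-man figures for transfusion (<1 to 5%) and recurrence (15 to 20%).
- A reader might infer that the trial will declare PRP safe on a zero count. The plan has no safety hypothesis, threshold or decision rule. That a bare zero may be over-read is a judgement about readers.

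It is also fair that an event-free trial is unlikely over 18 months after major surgery. The 0/20 figure therefore applies to individual categories, not to all adverse events together. Finally, this is a descriptive pilot; but an interval is itself descriptive and needs no hypothesis test.

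**Conclusion.** The point holds as an omission that should be corrected. For its primary objective the plan states a count and commits to no per-man proportion, interval or confidence level.

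Its size depends on the result. Once events occur, one count can correspond to quite different per-man risks. For an empty category, 20 treated men leave risks up to about 17% open at a two-sided 95% level (about 14% one-sided). Both limits rest on an assumed level and on exactly 20 treated men being counted. The withdrawal example shows the direction of a possible distortion; its size cannot be estimated from the documents.

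Nothing here shows that the sample is too small for a descriptive pilot or that the data collection is inadequate.

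**What to change.** 1. **Section 7.2.** State that the primary safety summary is the number and percentage of all PRP-treated men with at least one event, overall and by category, with exact two-sided 95% CIs. The categories should be local reaction, other non-serious adverse event, expected serious adverse event and unexpected serious adverse event. The second is needed because the Study Summary's list has no place for events such as the day-2 hemoglobin abnormality that section 8.1 defines as an adverse event. Event counts become supportive.

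2. **Sections 4.4.2, 4.4.3 and 7.3.** Reconcile these with the new summary so that a man who received PRP and later withdraws stays in the safety denominator with the data collected up to withdrawal. Men withdrawn during surgery before PRP is applied would not be in it. Replacement to reach 20 completers can continue, but the safety denominator may then exceed 20. Without this step, the words *treated men* in 7.2 would contradict the other sections.

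3. **Section 7.1.** Add that zero events in 20 treated men excludes only risks above about 17% (two-sided 95%), with the limit recalculated if more than 20 are treated.

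The cost is a few sentences across four sections and a less favourable-looking statement of precision. No extra data, visits or patients are needed.

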1.1 Background

Prostate cancer is a common problem worldwide with an estimated incidence of 1.1 million cases and 307, 000 deaths in 2012. Advancing age, black race, and poor health literacy are known risk factors for development of prostate cancer. Radical prostatectomy remains the most common surgical treatment for prostate cancer with excellent oncologic outcomes. With the development of anatomic RP, ED after surgery has decreased but the risk is still a significant treatment concern. Even with nerve-sparing RP, a significant proportion of man can experience transient or even permanent ED. The etiology of ED after nerve-sparing RP is multifactorial, however common factors contributing to the problem related to nerve damage secondary to thermal or mechanical trauma.¹⁻³

Recovery of sexual function after RP may depend on nerve healing or nerve-regrowth from the remaining NVB. Until now, this has been thought to be a time-dependent process. New evidence suggests that growth factors play an important role in this process. Platelets are known to contain many growth factors such as platelet-derived growth factor, insulin growth factor 1, vascular endothelial growth factor and transforming growth factor beta. At the time of RP, whole blood containing platelets and other hemostatic substances is observed to have an intraoperative impact on repairing the neurovascular bundle. At the time of RP, platelets are functioning in a homologous manner to counteract the surgical trauma required to remove the prostate. At the time of surgery, the platelets demonstrate a physiologic response by releasing growth factors to help repair the NVB.

Growth factors such as vascular endothelial growth factor, insulin growth factor -1, and brain-derived growth factor have been shown to promote neuronal regeneration and increase the presence neuronal nitric oxide synthase in cavernosal nerve tissue.¹ A prior report has evaluated the use of dehydrated human amnion/chorion membrane allograft nerve wrap as a means to deliver growth factors and anti-inflammatory substances during RP. In this study, allograft enhanced functional recovery yet this approach required placement of a foreign body.⁴

1.2 Investigational Agent

PRP is prepared by specialized centrifugation of a patient's own whole blood.⁵ The PRP product that is created is a platelet concentrate of approximately 1,000,000 platelets/mL. The morphology and function of the platelets in the whole blood sample used to create the product and morphology and function of the platelets in the prepared PRP sample are identical. In both instances during RP, the platelets are activated to release growth factors that help repair the NVB that is traumatized during surgery.

In general, platelets are known to contain many growth factors such as platelet-derived growth factor, insulin growth factor 1, vascular endothelial growth factor and transforming growth factor beta that can have a healing effect and regenerative effect on nerve tissue. By concentrating the number of platelets by volume, the healing and regenerative impact of PRP on the NVB is thought to be augmented. The basic function of the platelet is not changed, but the repairing effect on the NVB is increased by the fact that the concentration of the platelets compared to whole blood has been increased.

1.3 Preclinical Data

In animal models, application of PRP has promoted healing of cavernous nerves in an experimental nerve crush model when compared to controls.¹⁻³

1.4 Clinical Data to Date

To date, there is no available clinical research data on use of PRP application to the NVB intraoperatively at the time of nerve-sparing RP. Clinical application of PRP using a similar topical application, however, has been found to be safe and efficacious for a variety of musculoskeletal indications including osteoarthritis, chronic tendinopathy, nerve injury and ligamentous injuries.⁵⁻¹⁰

1.5 Dose Rationale and Risk/Benefits

The PRP sample will be prepared in the operating room from a sample of whole blood while the patient is undergoing RP. The PRP sample will be prepared by trained personnel from the Mayo Clinic Division of Transfusion Medicine using a commercially available, FDA-cleared, platelet concentration device in accordance with the manufacturer's instructions ((510K# BK110046; Angel® Concentrated Platelet Rich Plasma [cPRP] System, Cytomedix, Inc., Gaithersburg, MD USA). The Division of Transfusion Medicine has developed a detailed SOP that all staff using the Angel® system must follow in order to operate the Angel® device (http://mayoweb.mayo.edu/txmed-docs/documents/002696.pdf).

At the present time, the Angel® device is used in routine clinical use in the department of orthopedics and physical medicine and rehabilitation at Mayo Clinic. The Angel® system yields platelet concentrations of approximately 1,000,000 platelets/ mL of plasma. This dose of PRP has been demonstrated to have clinical efficacy and safety for topical applications used in orthopedic and physical medicine and rehabilitation applications.

Clinical experience with the Angel® device has demonstrated that a sample of 180 mL of whole blood will yield approximately 10 mL of PRP. This dose would be divided equally and will permit even topical application to the NVB intra-operatively at RP. The study proposes a one-time dosage period and clinical studies to date report that the duration of action for PRP is approximately 4 hours.

Risks from study participation may be related to obtaining the whole blood to produce the PRP sample or the effects of the PRP sample on the healing process after surgery. The collection of

blood would be obtained under general anesthesia required for RP using sites needed for the general anesthetic. Obtaining the whole blood could results in pain, bruising, and infection at the needle site. Obtaining a collection of blood could also have an adverse effect the patient's circulating blood volume and could result in lightheadedness or hypotension after surgery. In some instances this could require that a blood transfusion be given. Since the risk of blood transfusion for RP ranges from <1 to 5%, the independent risk of the blood collection alone requiring a postoperative blood transfusion is very low.

Platelets contain growth factors and the hypothesis of the study is that the growth factors will augment healing of the NVB after surgery. There is a possibility that the growth factors could cause adverse healing of the NVB. There is also a possibility that if residual prostate tissue is present that growth of the tissue could occur. There is a low risk that if the residual prostate tissue were cancerous that the growth factors could contribute to a higher chance of cancer recurrence. The relatively short term effect (<4 hours) of PRP applied topically will significantly decrease the risk of promoting growth of prostate tissue. It is also defined approximately 15-20% of men undergoing radical prostatectomy can expect to have recurrence after surgery. Based on the physiology of growth factors, it is thought the risk of PRP independently increasing risk of prostate cancer recurrence is very unlikely.

Benefits are thought to outweigh the risks of the study. Topical application of autologous PRP at the time of RP will permit supraphysiologic doses of growth factors to be present on the NVB. The growth factors may help promote healing and/or decrease the surgical trauma associated with RP. This may augment healing and recovery of erectile function after RP as measured during the 18 month study duration. Subjects will be asked to complete questionnaires regarding urological symptoms, quality of life (urinary control and ED) before and at 3, 6, 9, 12, and 18 months following the procedure.

2 Study Objectives

Primary Objective: To evaluate the safety and tolerability of using platelet rich plasma on the NVB after nerve-sparing radical prostatectomy.

Secondary Objective(s):

- To assess the feasibility of applying 1 dose of PRP intra-operatively at the time of bilateral nerve-sparing RP in 20 men with prostatic adenocarcinoma.
- To assess preliminary clinical benefit/efficacy of using PRP in facilitating early nerve healing and decreasing ED at 3, 6, 9, 12 and 18 months after nerve-sparing RP. To assess change in urological function by measuring urinary control before and at 3, 6, 9, 12 and 18 months after PRP treatment during nerve sparing surgery.

3 Study Design

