8.1 Definitions

Unanticipated Problems Involving Risk to Subjects or Others (UPIRTSO)

Any unanticipated problem or adverse event that meets the following three criteria:

- Serious: Serious problems or events that results in significant harm, (which may be physical, psychological, financial, social, economic, or legal) or increased risk for the subject or others (including individuals who are not research subjects). These include: (1) death; (2) life threatening adverse experience; (3) hospitalization inpatient, new, or prolonged; (4) disability/incapacity persistent or significant; (5) birth defect/anomaly; (6) breach of confidentiality and (7) other problems, events, or new information (i.e. publications, DSMB reports, interim findings, product labeling change) that in the opinion of the local investigator may adversely affect the rights, safety, or welfare of the subjects or others, or substantially compromise the research data, **AND**
- Unanticipated: (i.e. unexpected) problems or events are those that are not already described as potential risks in the protocol, consent document, not listed in the IB, or not part of an underlying disease. A problem or event is "unanticipated" when it was unforeseeable at the time of its occurrence. A problem or event is "unanticipated" when it occurs at an increased frequency or at an increased severity than expected, AND
- Related: A problem or event is "related" if it is possibly related to the research procedures.

Adverse Event

An untoward or undesirable experience associated with the use of a medical product (i.e. drug, device, biologic) in a patient or research subject.

Serious Adverse Event

Adverse events are classified as serious or non-serious. Serious problems/events can be well defined and include;

- death
- life threatening adverse experience
- hospitalization
- inpatient, new, or prolonged; disability/incapacity
- persistent or significant birth defect/anomaly

and/or per protocol may be problems/events that in the opinion of the sponsor-investigator may have adversely affected the rights, safety, or welfare of the subjects or others, or substantially compromised the research data.

All adverse events that do not meet any of the criteria for serious, should be regarded as **non-serious adverse events**.

Adverse Event Reporting Period

For this study, the study treatment follow-up period is defined as 18 months following the topical application of PRP at the time of RP.

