Preexisting Condition

A preexisting condition is one that is present at the start of the study. A preexisting condition should be recorded as an adverse event if the frequency, intensity, or the character of the condition worsens during the study period.

General Physical Examination Findings

At screening, any clinically significant abnormality should be recorded as a preexisting condition. At the end of the study, any new clinically significant findings/abnormalities that meet the definition of an AE must also be recorded and documented as an AE.

Post-study Adverse Event

All unresolved AEs should be followed by the sponsor-investigator until the events are resolved, the subject is lost to follow-up, or the AE is otherwise explained. At the last scheduled visit, the sponsor-investigator should instruct each subject to report, to the sponsor-investigator, any subsequent event(s) that the subject, or the subject's personal physician, believes might reasonably be related to participation in this study.

Abnormal Laboratory Values

A clinical laboratory abnormality should be documented as an AE if the serum hemoglobin on postoperative day 2 is <8 g/dL. If hemoglobin level is considered an AE, then patient should have hemoglobin monitored and if there is a downward trend or if clinical symptoms are associated with the value then blood transfusion should be considered.

Hospitalization, Prolonged Hospitalization or Surgery

Any AE that results in rehospitalization or prolonged hospitalization (greater than 1 week) should be documented and reported as a serious AE unless specifically instructed otherwise in this protocol. Any condition requiring surgery should be documented as an AE if the condition meets the criteria for an AE.

Neither the condition, hospitalization, prolonged hospitalization, nor surgery are reported as an AE in the following circumstances:

- The planned hospitalization for RP.
- The prolonged hospitalization for diagnosis not related specifically to RP.
- Surgical procedure not related to RP.

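### Recurrence, a harm the protocol itself attributes to PRP, is not defined as a safety outcome, and the withdrawal and replacement rules can remove a treated man who has it from the primary safety dataset

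*Combined protocol and SAP*

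**What the plan says.** **The risk.** Section 1.5 states that if residual tissue were cancerous, "the growth factors could contribute to a higher chance of cancer recurrence". It calls this risk low and gives a background figure: "approximately 15-20% of men undergoing radical prostatectomy can expect to have recurrence after surgery". No time horizon is attached to that figure.

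**The primary objective.** Section 3.2 gives the primary endpoint only as an objective: "To evaluate the safety and tolerability of using platelet rich plasma on the NVB". It lists no component measures. The Study Summary says "The safety evaluation will focus on the number of adverse events" and then, in the same cell, that oncologic outcomes will be assessed at 3, 6, 9, 12 and 18 months.

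**Data collected.** The schedule in section 6.8 has serum PSA at baseline, week 12 and months 6, 9, 12 and 18. Sections 3.1 and 8.6 plan to benchmark safety against registry patients, for whom PSA and oncologic data are held. Section 7.2 promises descriptive statistics for all variables but names only erectile function and continence as outcomes to follow over time.

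**AE rules.** The reporting period in section 8.1 is "18 months following the topical application of PRP at the time of RP". The one laboratory value given an AE rule is hemoglobin: "A clinical laboratory abnormality should be documented as an AE if the serum hemoglobin on postoperative day 2 is <8 g/dL". A worsening preexisting condition is also an AE. Recurrence is not mentioned.

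**Who is analysed.** Section 4.4.1 counts a man who discontinues after surgery as withdrawn. Section 4.4.2 excludes the data collected on withdrawn men from the analysis. Section 4.4.3 removes them from the final cohort and continues recruitment until 20 men complete 18 months. Section 7.3 evaluates consented subjects who complete postoperative visits. Section 5.6 lists androgen deprivation among treatments not permitted during the study.

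**The concern.** There are two gaps, and the second is the more serious.

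First, the late harm that the protocol itself raises is measured but not turned into a result. A table of PSA values by visit is not a count of recurrences. A comparison with registry patients needs one definition applied to both groups, and none is given. The safety conclusion could be written without a recurrence figure and still comply with the plan.

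Second, the analysis set for the primary safety objective depends on what happens after treatment. A man who received PRP, had a recurrence and then left the study would be taken out, with the data already gathered on him, and replaced by someone who completed follow-up. If leaving is related to recurrence or its treatment, the loss is selective and lowers the reported harm. The open question about androgen deprivation adds a second possible route to the same result.

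**Working it through.** **Step 1. What the plan's own figure can tell us.** Section 7.1 says "a sample of 20 subjects is proposed" and supports this as typical of such trials. It gives no error rate, power or precision target, so there is no calculation to reproduce. The figures below are illustrations at n = 20.

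**Step 2. Would events be expected?** Expected count = n × p, and P(at least one) = 1 − (1 − p)^20.

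| Recurrence probability p | Source | Expected in 20 | P(at least one) |
|---|---|---|---|
| 5% | assumed, by 18 months | 1.0 | 64.2% |
| 10% | assumed, by 18 months | 2.0 | 87.8% |
| 15% | section 1.5, no time horizon | 3.0 | 96.1% |
| 20% | section 1.5, no time horizon | 4.0 | 98.8% |

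Because the 15-20% has no horizon, the 5% and 10% rows are assumptions for a shorter follow-up. Across the whole range, at least one recurrence is more likely than not even if PRP has no effect.

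**Step 3. Follow one treated man through the rules.**

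1. He receives PRP. The intra-operative withdrawals in section 4.4.1 come before this point, so those men are not the issue.
2. His PSA rises during follow-up. No section says what rise is a recurrence, or whether it is an AE or SAE.
3. Route A: he chooses to stop. Section 4.4.1 makes him withdrawn, section 4.4.2 excludes his data, and section 4.4.3 replaces him. This follows from the text.
4. Route B: he is given androgen deprivation. Section 5.6 does not permit it during the study, and no section says what follows. If he is classed as withdrawn, he takes Route A. If not, he stays. The documents do not settle which.

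**Step 4. Effect of losing one event.** Suppose 21 men are treated and one man with recurrence is removed and replaced, so that 20 complete. Exact (Clopper-Pearson) 95% intervals:

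| All treated men | As reported after removal |
|---|---|
| 1/21 = 4.8% (0.1 to 23.8) | 0/20 = 0% (0 to 16.8) |
| 3/21 = 14.3% (3.0 to 36.3) | 2/20 = 10% (1.2 to 31.7) |

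The change is 4.8 percentage points in the first row and 14.3 − 10.0 = 4.3 in the second. In the first row the report changes from one recurrence to none.

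**Step 5. What a full count could show.** With nobody lost, 1/20 = 5% (0.1 to 24.9) and 3/20 = 15% (3.2 to 37.9). An illustrative one-sided 5% rule to detect a doubling from 15% to 30% flags at 7 or more events, with actual alpha 2.2% and power 39.2%. From 20% to 40% it flags at 8 or more, with alpha 3.2% and power 58.4%. Twenty men can describe the rate but could not reliably detect a doubling.

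**The case against.** The strongest reply is that recurrence is not ignored. The Study Summary plans oncologic outcomes at the five PSA time points, section 7.2 summarises all variables, and the registry benchmark in sections 3.1 and 8.6 rests on PSA and oncologic data. Section 8.2 requires all AEs to be recorded, and section 8.1 treats worsening of a preexisting condition as an AE. All of this stands.

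A reader might therefore go too far in two ways.

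- **That no recurrence would appear in the AE count.** The documents do not support this. The hemoglobin rule says when that value is an AE; it does not say nothing else can be. The general rules can capture a recurrence, but none ensures that they will.
- **That the phrase "not part of an underlying disease" in section 8.1 shuts recurrence out.** That wording belongs to the test for an unanticipated problem, which governs reporting. It is not in the AE or SAE definitions.

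It is also fair to object that no section makes androgen deprivation a ground for withdrawal. That stands too, so Route B is an unresolved question and not a stated rule. Route A does not depend on it.

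Finally, a named outcome in 20 men would have little power. This is true, and it is a reason to present the figure descriptively with its interval. It is not a reason to leave the figure undefined or to lose events from it.

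**Conclusion.** The point holds in two parts. Recurrence is collected for but left undefined, and it is not tied to the primary safety endpoint, the AE rules or section 7. That part is mainly missing detail. The weightier part is that stated rules remove and replace any treated man who withdraws after surgery, so a man with recurrence can leave the primary safety dataset.

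The size is one event at a time: about 4 to 5 percentage points per recurrence lost in a cohort of this size, and possibly the difference between reporting one recurrence and none. This assumes that one man with recurrence is withdrawn and replaced. How often that would happen cannot be derived from the documents. They do not show that it will happen, only that the rules allow it, and for a man who chooses to stop they require it. The event probabilities in the working rest on the protocol's 15-20%, which lacks a time horizon, or on an assumed 5-10% by 18 months.

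The plan should be changed on this point; it does not make the trial unsound.

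**What to change.** 1. **Safety set (sections 4.4.2, 4.4.3 and 7.3).** State that every man who received PRP stays in the safety analysis with all data collected on him, whatever happens later, including withdrawal, recurrence or treatment for it. Limit replacement to the efficacy cohort. Section 9.1 already notes that information collected before a subject revokes authorization may still be used.
2. **Reconcile sections 4.4.2, 4.4.3 and 5.6.** Say how the data of a man who receives androgen deprivation after recurrence are handled. This concerns the analysis set only; no change to clinical management is proposed.
3. **Outcome (sections 3.2 and 8.1).** Name PSA recurrence by 18 months as a safety outcome, with one definition fixed in advance and applied identically to trial men and registry comparators. State how a recurrence is classified in AE reporting.
4. **Analysis (section 7.2).** Report the number of recurrences among all treated men with an exact 95% interval, and label this and the registry comparison as descriptive. A Kaplan-Meier estimate is optional.

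The cost is a few sentences and no new tests, since PSA is already scheduled. The safety figures may look slightly less favourable, and the safety denominator may exceed 20.
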